12.5.5 Exploratory Endpoint Analysis

Exploratory efficacy endpoint analysis will be non-inferential in nature. The following endpoints will have summary statistics produced All analysis will be performed based on the observed case i.e. only subjects with data at the visit will be summarized in the analysis, which will be based on the FAS.

12.5.5.1 Change in Liver and Spleen Stiffness

Any data collected for liver and spleen stiffness measured using MRE (Protocol versions 1.0 to 4.0 only) will be listed, including change from baseline values. Any results collected during the extension phase will be flagged.

12.5.5.2 Change in Patient-Reported Outcomes

The change from baseline over the 24 week treatment period for the following patient-reported outcomes will be summarized:

- PBC 40 domains: Social Function, Cognitive Function, Emotional function, Symptoms (refer to Section 10.12)
- Overall health-related quality of life as assessed by the PROMIS-29 questionnaire (refer to Section 10.11).
- The MMRM analysis will be conducted for PROMIS-29 fatigue domain in the same manner as the change in fatigue (refer to Section 12.5.3.1). No sensitivity analysis will be performed.
- EQ-5D utility index (refer to Section 10.16)

Only summary statistics for the absolute and change from baseline scores will be presented.

12.5.6 Additional exploratory analyses

Additional exploratory analyses may be performed by the Sponsor to aid data interpretation:

- Scatter plots to show the correlation between QoL scores for fatigue at baseline versus change from baseline at week 24.
- Scatter plots to show the correlation between QoL scores for fatigue domains and AEs of fatigue.
- Scatter plots and summaries of change over time in fatigue and other QoL domains by severity of fatigue at baseline for PBC-40 (where mild <=28 and moderate/severe >=29)
- Imputation of (baseline) missing PROMIS short form fatigue 7b using the modelled relationship with the baseline PBC40 data
- Graphical presentation of changes in ALP, fatigue and liver stiffness where results from the PH2b study and the prior Ph2 study are combined in one plot.

12.6 Safety Analyses

12.6.1 Adverse Events

All AEs will be coded using MedDRA Version 24.0 or later. All AEs (including non-treatment-emergent and post-treatment events) recorded on the CRF will be listed. AEs that are not treatment emergent will be flagged for both treatment emergent definitions described in Section 10.7.1 and AEs that are assigned to the extension phase will also be flagged. Only TEAEs (see Section 10.7.2) will be included in AE summary tabulations unless otherwise specified. Summary tables of TEAEs will be presented by treatment group and

Version Date: 27-June-2024

Sponsor: Calliditas Therapeutics Suisse SA

Protocol No: GSN000350

total for the SS and repeated for both treatment emergent definitions. The National Cancer Institute common terminology criteria for Adverse Events (CTCAE) toxicity grading criteria version 4.03 will be used for toxicity grading of AEs.

All AE summaries will include the number and percentage of subjects in each category and the number of events. For the calculation of the incidence of events, subjects will only be counted once within the events. For summaries by SOC and PT, subjects will be counted once per unique PT and SOC. For summaries by SOC and PT tables should be sorted in descending order of SOC and then PT by subject counts in the total group.

An overall summary of TEAEs will be presented with the following categories:

- Any TEAEs
 - TEAEs related to IMP
- Any severe TEAEs (CTCAE Grade 3 or greater)
 - o Any severe TEAEs (CTCAE Grade 3 or greater) related to IMP
- Any TESAEs
 - Any TESAES related to IMP
- TEAEs with outcome of death (events with outcome of Fatal on the AE CRF page)
 - o TEAEs related to IMP with outcome of death
- TEAEs leading to discontinuation of study treatment
 - TEAEs related to IMP leading to discontinuation of study treatment
- TEAEs leading to modification of study treatment
 - TEAEs related to IMP leading to modification of study treatment
- TEAEs leading to study discontinuation
 - o TEAEs related to IMP and leading to study discontinuation
- TEAEs of special interest
 - TEAEs of special interest related to IMP
- TEAEs requiring Adjudication
- TEAE related to Hepatic Encephalopathy (as indicated by the Investigator on the AE CRF page)

The following summaries will be presented by SOC and PT:

- TEAEs
- TEAEs by Maximum CTCAE Grade
- TEAEs related to IMP
- TEAEs related to IMP by Maximum CTCAE Grade
- TEAEs of special interest
- TEAEs of special interest related to IMP
- TEAEs leading to discontinuation of study treatment
- TEAEs leading to study discontinuation
- TESAEs

Sponsor: Calliditas Therapeutics Suisse SA

Protocol No: GSN000350

- TESAEs related to IMP
- Severe TEAEs of CTCAE Grade 3 or higher
- Non-Serious TEAEs
- TEAEs occurring in 2 or more of subjects (based on PT) in any treatment arm and summarized by PT only in descending order

Subjects with multiple events within a particular SOC or PT will be counted under the category of their most drug-related event within that SOC or PT (first order by drug-related).

Subjects with multiple events within a particular SOC or PT will be counted under the category of their most severe event within that SOC or PT (subsequent order by severity).

A listing of all AEs will be produced with treatment emergent flags for each treatment emergent definition (Sections 10.7.1 and 10.7.2). Separate listings of TEAEs leading to death, leading to IMP discontinuation, CTCAE grade 3 or higher TEAEs, AESIs and SAEs will be provided.

12.6.2 Adjudicated Events

The following adverse clinical outcomes will be adjudicated during the study:

- All-cause mortality/Death
- Variceal bleed
- Portal hypertension bleed
- Hepatic encephalopathy (West Haven criteria)
- Spontaneous bacterial peritonitis
- Uncontrolled ascites requiring treatment

Additionally, events that require IMP interruption (DILI, anemia and hypothyroidism) will also be adjudicated.

The proportion of subjects with adjudicated events in the above categories will be summarized in the SS. All subjects with adjudicated events will be listed.

An additional summary will be produced summarizing the proportion of subjects experience the following (not necessarily adjudicated) Safety events.

- progression to cirrhosis
- death (all-cause)
- liver transplant
- MELD ≥15 if the baseline MELD score was <12
- new onset ascites requiring treatment (diuretics or paracentesis),
- development of large varices if no varices at baseline,
- hospitalization due to a decompensatory event (for example, variceal bleeding, hepatic encephalopathy, spontaneous bacterial peritonitis)

If no such events are reported, this table will not be included.

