#### 5.4 Adverse Clinical Outcomes

The following adverse clinical outcomes will be captured during the study:

- All-cause mortality
- Patients requiring a liver transplant (transplant list inclusion)
- MELD score of ≥15 (confirmed at repeat testing at least 14 days apart), as calculated by the central laboratory, according to the formulas in Appendix III

The MELD score will be calculated based on the results from the liver biochemistry (total bilirubin), biochemistry (creatinine, and sodium if MELD score >11), and hematology (INR) blood samples, collected as described in Section 5.3.2.

- Variceal bleed
- Portal hypertension bleed
- Hepatic encephalopathy (West Haven criteria), see Appendix IV
- Spontaneous bacterial peritonitis
- Uncontrolled ascites requiring treatment

In the event of any of these outcomes, IMP will be permanently discontinued, as noted in Section 4.4.1, and the patient may continue study visits.

Investigators will record the AEs in the Adverse Event page of the eCRF and will indicate on the Adverse Event page if it meets the criteria for an SAE. If the event meets

the criteria of an SAE, it will be reported using the paper safety report form within 24 hours of becoming aware of the event.

The adverse clinical outcomes will be adjudicated by the Adjudication Committee (see Section 9.4.1).

Investigators will indicate on the eCRF Adverse Event page if the event meets the criteria for adjudication. If the event meets the criteria for adjudication, the Investigator will then complete the Adjudication Event eCRF.

Please refer to the Investigator adjudication manual for further information.

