## 9.4 Adjudication Committee and Independent Data Monitoring Committee

## 9.4.1 Adjudication Committee

The Adjudication Committee, who will remain blinded to patient treatment assignment, will adjudicate the AESIs (DILI, anemia, and hypothyroidism), and the following adverse clinical outcomes, which will require permanent IMP discontinuation: all-cause mortality, transplant list inclusion, MELD score of  $\geq 15$  (confirmed at repeat testing at least 14 days apart), variceal bleed, portal hypertension bleed, hepatic encephalopathy, spontaneous bacterial peritonitis, and uncontrolled ascites requiring treatment. These events will be adjudicated as defined in an Adjudication Charter.

Expert adjudication of cases will be conducted using the CIOMS/RUCAM (Council for International Organizations of Medical Sciences/Roussel Uclaf Causality Assessment Method) score, as well as detection of Hy's Law cases. Data from eDISH analysis will be provided to the Adjudication Committee.

An aggregated list of adjudicated events will be regularly provided to the IDMC for review.

The roles and responsibilities of the Adjudication Committee will be outlined in the Adjudication Charter.

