10.9 Adverse Clinical Outcomes

A subject has an adverse clinical outcome if any of the following criteria are met:

- Death
- Transplant list inclusion
- MELD score ≥ 15 (confirmed at repeat testing at least 14 days apart)
- Variceal blead
- Portal hypertension bleed
- Hepatic encephalopathy
- Spontaneous bacterial peritonitis
- · Uncontrolled ascites requiring treatment

Version Date: 27-June-2024

Sponsor: Calliditas Therapeutics Suisse SA

Protocol No: GSN000350

Subjects who discontinue treatment due to adverse clinical outcomes will be identified via medical review and provided to statistics prior to database lock.

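### SAP 12.6.2 tabulates six of the eight adverse clinical outcomes sent to adjudication; transplant listing and confirmed MELD of 15 or more are left out without explanation

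*SAP*

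**What the plan says.** Protocol 5.4 (Adverse Clinical Outcomes) lists eight outcomes. One is inclusion on a transplant list; another is "MELD score of ≥15 (confirmed at repeat testing at least 14 days apart), as calculated by the central laboratory". The section then refers the whole set to the committee, with no exceptions: "The adverse clinical outcomes will be adjudicated by the Adjudication Committee (see Section 9.4.1". Protocol 9.4.1 names the same eight as the committee's remit, in a sentence that includes "which will require permanent IMP discontinuation: all-cause mortality, transplant list inclusion, MELD score of" 15 or more.

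SAP 10.9 repeats the eight as its definition of an adverse clinical outcome. SAP 8.0 states that the Adjudication Committee adjudicates the adverse clinical outcomes, again without exception.

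SAP 12.6.2 (Adjudicated Events) introduces its list with "The following adverse clinical outcomes will be adjudicated during the study" and gives six. It adds drug-induced liver injury, anemia and hypothyroidism, and then says: "The proportion of subjects with adjudicated events in the above categories will be summarized in the SS" (SS is the safety analysis set). A further summary in the same section covers safety events that need not have been adjudicated. It has a line for liver transplant and a line reading "MELD ≥15 if the baseline MELD score was <12".

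The exploratory endpoints in SAP 9.4 include the proportion requiring a liver transplant, glossed as transplant list inclusion, and the proportion with a MELD score of 15 or more.

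**The concern.** The SAP's rule for the adjudicated-event table disagrees with the protocol and with two other sections of the SAP. Because the table is limited to the categories printed above it, an outcome missing from the list is also missing from the output. Programmed as written, the SAP gives no proportion for transplant listing and no proportion for confirmed MELD of 15 or more.

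Transplant listing and MELD of 15 or more are also named exploratory endpoints, so a reader of the study report would look for them. There is also a reconciliation problem. SAP 12.5.4.1 makes a patient with an adverse clinical outcome before Week 24 a non-responder for the cholestasis markers. Under the SAP 10.9 definition, a confirmed MELD of 15 or more would change a patient's responder status and yet appear in no row of the adjudicated-outcome table.

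**Working it through.** No sample size, power or error rate is involved. The check is an item-by-item comparison of four lists.

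| Outcome | Protocol 5.4 | Protocol 9.4.1 | SAP 10.9 | SAP 12.6.2, adjudicated list |
|---|---|---|---|---|
| Death from any cause | yes | yes | yes | yes |
| Transplant list inclusion | yes | yes | yes | **no** |
| MELD ≥15, confirmed at least 14 days apart | yes | yes | yes | **no** |
| Variceal bleed | yes | yes | yes | yes |
| Portal hypertension bleed | yes | yes | yes | yes |
| Hepatic encephalopathy | yes | yes | yes | yes |
| Spontaneous bacterial peritonitis | yes | yes | yes | yes |
| Uncontrolled ascites requiring treatment | yes | yes | yes | yes |
| Count | 8 | 8 | 8 | 6 |

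The difference is 8 − 6 = 2, and the two are the same against each of the other lists.

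**Is the removal declared?** SAP 6.1 (Changes from Protocol) has two entries, on the per-protocol set and on abnormal laboratory summaries. Neither concerns adjudicated outcomes.

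**Are the two outcomes tabulated elsewhere?** SAP 12.5.5, the exploratory endpoint section, covers liver and spleen stiffness by MRE and patient-reported outcomes. It contains no analysis of adverse clinical outcomes. SAP 12.6.3 flags MELD of 15 or more in listings, which gives no proportion. SAP 12.6.1 counts adverse events requiring adjudication, but not by type of outcome.

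**Does the second table in 12.6.2 stand in for them?**

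- Transplant: the row names the transplant itself, while the endpoint and the outcome definition are met by listing. Read literally, a patient listed but not transplanted within the period is not counted.
- MELD: the row requires baseline MELD below 12. Neither the SAP 9.4 endpoint nor the SAP 10.9 definition has that condition. Exclusion criterion 3 (Protocol 4.2) bars a MELD score of 12 or more except in patients on anticoagulants, so a group of eligible patients can never be counted in this row.
- The table is dropped altogether if none of its events is reported, so a zero count for a named endpoint would not be shown.

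**The case against.** The strongest reply is that little is lost. SAP 12.6.2 lists all subjects with adjudicated events, in a sentence that is not limited to the six categories. SAP 12.6.3 flags every MELD of 15 or more in listings with no baseline condition, and discontinuations due to adverse clinical outcomes are identified by medical review before lock (SAP 10.9). This stands: a reader might infer that such events would vanish from the report, and they would not. What is missing is the tabulated proportion.

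Four further limits on the point also stand.

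- A reader might infer that SAP 10.9 itself calls the two outcomes adjudicated. It only defines them as adverse clinical outcomes. The statement on adjudication comes from SAP 8.0 and from Protocol 5.4 and 9.4.1.
- A reader might fault the second table's MELD row for not requiring confirmation. That is not a defect against the endpoint: SAP 9.4 and Protocol 2.3 ask only for a score of 15 or more. The 14-day confirmation belongs to the adverse-clinical-outcome definition. The row's departure from the endpoint is the baseline limit. It follows that adding a confirmed MELD row alone would not tabulate the endpoint.
- MELD comes from scheduled laboratory tests, so one might infer that it is likely to be the outcome that occurs. The documents give no rate, and eligibility excludes prior decompensation, Child-Pugh of 6 or more, and (except on anticoagulants) MELD of 12 or more.
- The liver transplant row could be shorthand for listing, since the protocol's own endpoint glosses one with the other. If so, the wording is ambiguous rather than wrong, and it still needs settling.

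The reply does not explain why the lists differ.

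**Conclusion.** The discrepancy holds: two of eight adjudicated adverse clinical outcomes are absent from the SAP's adjudicated list and table, with no recorded reason. Read literally, the SAP yields no proportion for transplant listing and only a baseline-restricted one for MELD of 15 or more, although both are SAP 9.4 endpoints.

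The consequence is small. It touches reporting of exploratory and safety outcomes in a study planned for 60 to 70 patients, with few events expected. The documents give no count of anticoagulated patients with baseline MELD of 12 or more, so the reach of the baseline limit cannot be sized beyond saying that it affects that subset. The primary analysis and its error control are unaffected.

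The conclusion assumes that the table is programmed from the text of 12.6.2. A reader might go further and infer that the committee will not review these two outcomes. The documents do not support that: the protocol and SAP 8.0 say that it will, and the Adjudication Charter, which governs the process, is not available here. The defect shown is in the SAP text.

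**What to change.** 1. In SAP 12.6.2, add transplant list inclusion and MELD of 15 or more, confirmed at least 14 days apart, to the adjudicated list and its table, worded as in SAP 10.9.
2. Tabulate the SAP 9.4 endpoint, the proportion with MELD of 15 or more, without the baseline condition, and report it even when the count is zero. The existing row for baseline below 12 can stay as a separate item if it is wanted.
3. State whether the liver transplant row means the operation or listing.
4. If leaving the two outcomes out was deliberate, record and justify that in SAP 6.1 instead of making change 1. Change 2 is still needed, as is a tabulated proportion for the transplant-listing endpoint.

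The cost is two bullets and two rows for the adjudicated table, one row for the unrestricted MELD endpoint, and a wording clarification. No new data are needed: Protocol 5.4 already captures both outcomes, and the central laboratory supplies the MELD score.

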12.6.3 Laboratory Data

Laboratory data will be reported in Système International (SI) units.

Version Date: 27-June-2024

Sponsor: Calliditas Therapeutics Suisse SA

Protocol No: GSN000350

For clinical biochemistry, hematology and liver function tests (Table 8), shift tables from baseline to worst CTCAE grade on treatment will be produced for the SS, with separate summaries for each treatment period. Only parameters which have toxicity grading will be summarized. WBC and reticulocyte

counts will be expressed in absolute values. Differential count will be expressed as both absolute count and percentage of WBCs. Only central lab data will be included in the table summaries. All lab data collected locally and centrally will be listed.

Table 8: Laboratory Tests

Laboratory Tests	Parameters
Hematology	Hematocrit; hemoglobin; absolute and relative reticulocyte counts, red blood cell (RBC) count; white blood cell (WBC) count; differential WBC count; platelet count; absolute neutrophil count; mean cell volume, INR
Biochemistry	Glucose; total protein; creatinine; urea; total cholesterol; triglycerides; sodium; potassium; chloride
Liver Function	Serum fibrinogen, albumin, ALP, ALT, AST, total and conjugated bilirubin, GGT, hsCRP, lgM

To further examine the liver function tests collected during the study, suspected drug-induced liver injury (sDILI) summaries will be produced. Proportion of subjects meeting any of the following criteria for any post-baseline assessments will be presented for the SS, for each treatment period:

- AST or ALT ≥3xULN
- AST or ALT >2xBaseline
- Total bilirubin >2xULN
- INR>1.5

Any subjects with any of the above criteria for sDILI or cholestasis will be flagged in the listings. Subjects at risk of a drug induced liver injury according to Hy's law will also be flagged. Hepatic function abnormality defined by an increase in AST and/or ALT to \geq 3xULN concurrent with an increase in total bilirubin to \geq 2xULN but without increase in ALP (i.e., ALP < 2xULN) meets the criteria for Hy's law and raises the concern for DILI.

The MELD score will be calculated by the central laboratory based on the results from the liver biochemistry (total bilirubin), biochemistry (creatinine), and hematology (INR) blood samples. Subjects with a MELD score of \geq 15 will be flagged in the listings.

Data from the Extension Phase will be restricted to the period while a subject was on active and change from baseline comparisons using the extension baseline.

Table 9: Other Laboratory Tests

Laboratory Tests	Parameters
Markers of Liver Fibrosis	ELF score components for calculation of ELF score (TIMP-1, PIIINP, and hyaluronic acid) and the other PBC-related biomarkers (PRO-C3 and C3M; PRO-C3/CRM ratio)
Markers of bile acid metabolism	Total bile acids, C4, FGF19, FGF21
Autoantibodies	AMA titer, PBC-specific antibodies (anti-GP210, anti-SP100, antibodies against major M2 components [PDC-e2, 2-oxo-glutaric acid dehydrogenase complex])

Sponsor: Calliditas Therapeutics Suisse SA

Protocol No: GSN000350

Laboratory Tests	Parameters	
Viral Serology	HIV antibodies (1 and 2) and, if positive for HIV antibodies, HIV RNA; Hepatitis B surface antigen and hepatitis C virus antibodies and, if positive for HCV antibody, HCV RNA	
Pregnancy test	Serum pregnancy test; urine Pregnancy test	
Thyroid function	TSH and free T4	
Drug Screen (Urine)	Urine drug screen	
Urinalysis	pH; protein; glucose; ketones; bilirubin; blood; microscopic examination of the sediment	

Refer to Table 98, for a list of other laboratory parameters to be collected on this study and the laboratory test category each parameter will be summarized under. Autoantibodies, viral serology, pregnancy test, and drug screen parameters will be listed only. Markers of liver fibrosis, markers of bile acid metabolism, urinalysis, thyroid function will be summarized descriptively by scheduled visit using the SS.

Standard ranges from the central laboratory will be used for the laboratory analysis. The assessment as to if a lab test is low, high, normal as applicable will be derived using the standard ranges for central lab data. Laboratory data outside study-specific reference ranges will be listed.

Abnormal laboratory values, defined as values outside the normal range, will be listed by subject. Summaries of the incidence and frequency by treatment group and scheduled visit will be presented.

12.6.4 eDISH Analysis

Evaluation of drug-induced serious hepatotoxicity (eDISH) analysis will be conducted in order to explore potential liver toxicity signals by treatment group. A eDISH plot will be produced, which will display for each subject during the treatment period the maximal total ALT/AST value (expressed as a multiple of the ULN) against the maximal Total Bilirubin value (expressed multiple of the ULN) to identify possible values above Hy's law range. The plot will be produced using the SS and treatment period of 52 weeks (Section 10.7.1) and will display the maximal on-treatment value of ALT/AST and total bilirubin.

